This study (Figures 1 and 3) will include Option A consisting of 9 lab visits each approximately 2 hours long, except visit 1, which will last up to 3 hours **OR** Option B consisting of 5 lab visits each containing 2 vaping sessions separated by a 3-hour washout period and lasting approximately 6 hours. Figure 2 illustrates the study e-cig and e-liquid variations. Figure 3 depicts the sequence of the proposed study. We will conduct an experimental study examining how the manipulation of nicotine form (nicotine salt (NSB) vs. free-base (FB)) influences vaping behavior, abuse liability, toxicant exposure and heart and lung health.

Evaluating E-Cigarette Nicotine Form, Concentration, and Flavors among Youth

Figure 1. Vaping Session

Vaping Session	
12 hour nicotine abstinence	
Start of Session:	Surveys Respiratory Measures Cardiovascular Measures Blood Draw (0 min)
STD Puffing (5 min):	Blood Draw (5 min) Surveys
Ad-lib Puffing (30 min): Blood Draw (10 min) Blood Draw (35 min) Surveys	
3-hour washout (Visits 2-5 between vape sessions) (Option B Only)	
3 hrs. post exposure:	Respiratory Measures Cardiovascular Measures (Option B Only)
1 vaping session will occur at each visit for 9 visits (Option A Only)	
1 vaping session will occur at the first visit / 2 vaping sessions will occur at the final 4 visits (Option B Only)	

Figure 2. E-cig and e-liquid for Vaping Sessions

[figure not shown]
[figure not shown]

Figure 3. Study Sequence Option A and Option B

Evaluating E-Cigarette Nicotine Form, Concentration, and Flavors among Youth

ii. Study Procedures

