participants will use a study e-cig held at a constant wattage, and pre-filled with e-liquid of different nicotine form (free-base vs. nicotine salt), concentration (low-1% vs. high-5%), and flavoring (tobacco vs. menthol). There is no known commercial pair of nicotine liquids that differ only by nicotine form. For this study, we will prepare 8 e-liquids that differ by nicotine form, nicotine concentration, and flavor, simulating characteristics of popularly used nicotine liquids^{32, 39}. Prior to each visit, e-liquids will be prepared from pure (≥99%) S-(-)-nicotine; protonation and dilution of nicotine will be done using USP grade benzoic acid, and glycerol and propylene glycol, respectively.

E-cig abuse liability will be measured across several domains during and after the vaping session. During the vaping session, e-cig puff topography will be measured to produce measures of puff count, puff duration, inter-puff-interval, puff flow rate, average puff volume, and total puff volume⁵⁰. Post vaping session, subjective effects including the Drug Effects/Liking Questionnaire and modified Cigarette Evaluation Questionnaire (mCEQ)^{51, 52} will be conducted.

Next, behavioral economic demand will be assessed using the E-Cigarette Purchase Task⁵³ and E-Cig craving/suppression of craving and withdrawal will be assessed using the Tiffany-Drobes Questionnaire of Smoking Urges: Brief Form⁵⁴, and the Minnesota Nicotine Withdrawal Scale⁵⁵..

E-liquid consumption will be determined by weighing (mg) the participant e-liquid pod before and after the vaping session. To estimate toxicant exposure, the e-cig device, e-liquid, and participants' average puffing topography data for that e-liquid (across all participants) will be used to control a vaping machine. The e-cig aerosol produced will be collected on filters or in impingers for later analysis using high performance liquid chromatography, gas chromatography/mass spectrometry or similar methods of instrumental analysis.

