
Evaluating E-Cigarette Nicotine Form, Concentration, and Flavors among Youth

in airway inflammation immediately follow e-cig use⁴⁸. Airway reactivity will be measured via TremoFlo, which is a well validated measurement of central obstruction, peripheral obstruction, and dynamic collapse⁴⁹ and provides curves of Resistance (R) and Reactance (X) as well as parameters reflecting large and small airway function. The current literature shows an increase in impedance, respiratory resistance and overall peripheral airway resistance following e-cig use⁴⁸. Markers of endothelial dependent and independent function will be measured by B-mode ultrasound⁴⁴. Arterial stiffness, blood pressure, and heart rate will be measured at baseline. Arterial stiffness and vascular reactivity will be measured with pulse wave velocity (Vicorder or similar) and pulswave-analysis (AiX75, SphygmoCor or similar)⁴⁵. Inflammation will be measured by plasma levels of IFN- β , IL-1 β , IL-17, TNF- α as well as markers of oxidative stress, including OxLDL and Malondialdehyde⁴⁶

Evaluating E-Cigarette Nicotine Form, Concentration, and Flavors among Youth

Table 1: Project 3 Sub-study 2 Study Measures		
Project/Study	P3S2	
Visit	1	2-9 (Option A) or 2-5 (Option B)
Background Measures		
Sociodemographic Measures	X	
Tobacco Use History & Sensory E-Cigarette Expectancies Scale (SEES)	X	
E-Cig Dependence (modified Cigarette Dependence Scale)	X	
Timeline Followback (week, month, lifetime)	X	
E-cig Abuse Liability		
EC Puff Topography (puff count, puff duration, inter-puff interval, puff flow rate, average puff volume, total puff volume)	X	X
Subjective Effects		
Drug Effects/Liking Questionnaire	X	X
modified Cigarette Evaluation Questionnaire (mCEQ)	X	X
Sensory E-Cigarette Expectancies Scale	X	X
Behavioral Economic Demand		
E-Cigarette Purchase Task	X	X
E-cig Craving/Suppression of Craving and Withdrawal		
Tiffany-Drobes Questionnaire of Smoking Urges: Brief Form	X	X
Minnesota Nicotine Withdrawal Scale Self-Report	X	X
Nicotine Uptake		
Forearm Venous Catheter	X	X
E-liquid Consumption		
e-liquid containers for pods will be weighed	X	X
Toxicant Exposure		
Average topography “puff playback,” and e-cig aerosol produced and collected on filters	X	X
Liquid and Gas Chromatography/Mass Spectrometry	X	X
E-cig Device Characteristics		
Device voltage, coil resistance, pressure drop	X	X
E-liquid Characteristics		
pH, nicotine concentration, and PG/VG ratio	X	X
Physiological Effects (Pulmonary)		

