Laboratory Spirometry (SpiroLab)	X	X
Airway Inflammation (NIOX VERO)	X	X
Airway Reactivity (TremoFlo)	X	X
Cardiovascular Measures		
Vascular Reactivity (Vicorder or similar)	X	X
Blood Pressure	X	X
Heart Rate	X	X
Markers of endothelial dependent and independent function		
B-mode ultrasound (Vicorder or similar)	X	X
Arterial stiffness		
Pulse wave velocity and analysis (Vicorder or similar)	X	X

Evaluating E-Cigarette Nicotine Form, Concentration, and Flavors among Youth

E. Statistical Methods

Generalized linear mixed models will be employed to identify associations of nicotine form, nicotine concentration, and flavoring with various outcome measures (e.g., plasma nicotine, spirometry, flow-mediated dilation). Models will include relevant covariates (e.g., gender), a random effect for participant, main effects for nicotine form and concentration, and the interaction between nicotine form and concentration and nicotine form and flavor. Because of multiple measurements tested, we will assume a significance threshold corresponding to one expected false discovery per 100 tests ($p=0.01$).

i. Power Analysis

This study, for each of the main effects and $\alpha = 0.01$, achieves 80% power to detect an effect size of 0.5 standard deviations of the paired differences. For interaction effects, we will estimate 80% power (effect size 0.5 SD) to distinguish between any two of the interaction groups (e.g., free base/low nic, free base/high nic), while correcting for the pairwise tests ($p=0.01/6=0.0017$). Carryover and period effects will also be examined.

ii. Data Analytic Plan

Because product sampling will be randomized using a Latin Square, a fixed effect for session and a random effect for sequence will be included in all analyses.

iii. Missing Data

While we will make every effort to minimize the missing data for this study, missing data can arise due to various reasons. Violation of missing complete at random (MCAR) will be checked by evaluating whether any covariates are associated with missing data. If so, these covariates will be subsequently included and controlled for in the GLMM model. Our primary analysis will use mixed models which assumes Missing At Random (MAR) to deal with the missing data problem. In addition, sensitivity analyses will also be conducted using results from multiple imputation and complete cases strategies.

F. Gender/Minority/Pediatric Inclusion for Research

i. Inclusion of Women and Minorities

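### The plan does not tie craving and withdrawal suppression to a pre-vaping score, which costs precision and leaves second sessions in Option B open to carryover

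*Combined protocol and SAP*

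**What the plan says.** Section D.iii lists craving, its suppression and withdrawal as the fourth abuse-liability domain, and H1b and H1c both make claims about abuse liability.

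On timing, Section D.ii.2.a says "E-cig abuse liability will be measured across several domains during and after the vaping session". It gives the liking and evaluation questionnaires after the session and then continues: "E-Cig craving/suppression of craving and withdrawal will be assessed using the Tiffany-Drobes Questionnaire of Smoking Urges", together with the Minnesota withdrawal scale. It names no administration before vaping.

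Figure 1 (Section D.i) opens every session with "Surveys Respiratory Measures Cardiovascular Measures Blood Draw (0 min" and shows surveys again after the standardized and the ad libitum puffing. It does not say which instruments are in each slot. Table 1 marks the two scales by visit, with no time point inside a session.

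On analysis, Section E says "Models will include relevant covariates (e.g., gender), a random effect for participant", and then "main effects for nicotine form and concentration, and the interaction between nicotine form and concentration and nicotine form and flavor". Section E.ii adds that "a fixed effect for session and a random effect for sequence will be included in all analyses". Section E.i says carryover and period effects will be looked at, without a method. Nothing defines suppression or mentions a pre-session score or a change score.

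**The concern.** Suppression is a fall from a starting level. If the scales are given only after vaping, or are given before as well but the earlier score is not used, the analysed quantity is the craving level after vaping.

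A participant effect removes stable differences between people but not changes within a person from session to session. In Option B some of those changes are built in. The 12-hour abstinence in Section D.ii precedes each visit. The second session of a visit follows a 3-hour washout whose stated purpose concerns nicotine levels, not craving. (Section G.ii counts nine occasions of 12-hour abstinence, which does not match the five Option B visits; the two sections must be reconciled.) Participants choose their option, so one session effect is shared by people who start the same session number in different states.

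At stake are the precision of one abuse-liability domain, a possible distortion of liquid effects in Option B, and freedom to choose between post-score, change score and adjusted score after seeing the data. A pre-vaping score that is not collected cannot be recovered later.

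**Working it through.** **1. The plan's own power figure.** Inputs from Sections D.ii and E.i: 60 completers, alpha 0.01 for main effects, 0.01/6 = 0.0017 for pairwise interaction contrasts, effect 0.5 SD of the paired differences. Two-sided tests are assumed, since sidedness is not stated. The noncentrality is 0.5 × √60 = 3.87.
- Main effects: power 90% (normal) or 88% (t), so the stated 80% is conservative.
- Pairwise contrasts: 77% (normal) or 71% (t), below the stated 80%.

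**2. Gain from the pre-score.** Let r be the within-person correlation of pre- and post-vaping scores. No document gives it, so a range is assumed. Residual variance is multiplied by 1 − r², the sample-size equivalent is 1/(1 − r²), and the standardized effect becomes 0.5/√(1 − r²). Power is t-based at N = 60.

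| r | 1 − r² | Variance cut | 1/(1 − r²) | Effect | Power, main | Power, pairwise |
|---|---|---|---|---|---|---|
| 0 | 1.00 | 0% | 1.00 | 0.500 | 88% | 71% |
| 0.3 | 0.91 | 9% | 1.10 | 0.524 | 91% | 77% |
| 0.5 | 0.75 | 25% | 1.33 | 0.577 | 96% | 87% |
| 0.6 | 0.64 | 36% | 1.56 | 0.625 | 98% | 93% |

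**3. A raw change score is not a safe substitute.** With equal pre and post variances its effect is 0.5/√(2(1 − r)). At r = 0.3 this is 0.5/1.183 = 0.423, with 73% main-effect power against 88% for the post-score alone. The two are equal at r = 0.5.

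**4. Is the unadjusted post-score biased?** An eight-period Latin square was simulated with 64 participants, a true concentration effect of −0.50 and a pre-to-post slope of 0.5, with person and session effects removed.
- Starting craving varying at random, or 1 to 2 SD lower in Option B second sessions: the unadjusted estimate stayed at about −0.50. Its standard error was about 0.09, against 0.077 with the pre-score. The variance ratio (0.077/0.09)² = 0.73 agrees with 1 − r² = 0.75 at r = 0.5.
- Second-session craving also 1 SD lower after a high-concentration liquid (assumed): under some layouts the unadjusted estimate shrank to about −0.38 with half the participants in Option B and −0.25 with all of them. Under other layouts it stayed at −0.50. The adjusted estimate was −0.50 throughout.

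**5. Why layout decides.** In the affected layouts every visit paired one low with one high liquid, so a low liquid in second place always followed a high one. The shift is slope × carryover × share of second sessions: 0.5 × 1 × 0.5 = 0.25 with everyone in Option B, and 0.5 × 1 × 0.25 = 0.125 with half. Then −0.50 + 0.25 = −0.25 and −0.50 + 0.125 = −0.375. In the unaffected layouts the four low/high orders within a visit were equally frequent. A square balanced for carryover over all adjacent sessions (a Williams square) fell into either group depending on how liquids were assigned to its labels. The balance that matters is therefore within visits. The text does not describe the square; Figure 3 was not available for this check.

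**The case against.** A reader might infer that the scales are given only after vaping and that the analysis treats every session as starting from the same craving level. The documents support neither statement.

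- Table 1 confines the background questionnaires to visit 1, so the opening survey slot at later visits must hold repeated instruments, and the urge and withdrawal scales are natural candidates. That is inference, and Section D.ii.2.a points the other way, but pre-vaping administration cannot be ruled out.
- The covariate list in Section E is open, with gender only as an example. A pre-score is unspecified, not excluded.
- Session effects absorb average differences between sessions, and the randomized order spreads the rest over the liquids. Ordinary variation in starting craving therefore adds noise and does not bias the comparison.
- Carryover is to be examined, and in Option A each session is its own visit after 12 hours of abstinence.
- The size of the gain rests on an assumed r, and main-effect power already exceeds the stated 80%.

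All of this stands and limits the point. It does not close the gap: the instruments in the opening slot are unnamed, suppression is undefined, use of a pre-score is left open, and the carryover examination has no method. The pairwise contrasts, where power falls short, are where added precision helps most.

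**Conclusion.** The point holds as a gap in specification. Followed as written, the plan does not measure suppression against a starting level. The main consequence is lost precision: 9% to 36% of residual variance for r from 0.3 to 0.6, equivalent to 10% to 56% more participants for these outcomes. All of that depends on the assumed r.

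A general claim that the post-score analysis is biased, or that the previous liquid's effect is read as the current one's, goes beyond the documents. Bias by this route needs three things together: an Option B second session, starting craving that depends on the preceding liquid, and an order that does not balance the liquids paired within a visit. The shrinkage from −0.50 to −0.38 or −0.25 illustrates that case under an assumed 1 SD dependence; it is not a forecast. The pre-score removed it because the simulated carryover acted only through starting craving; carryover by another route would remain.

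**What to change.** 1. Reconcile Figure 1 with Section D.ii.2.a: state that both scales are given in the existing start-of-session survey slot of every session as well as after vaping. Show both time points in Table 1.
2. In Section E, for the craving and withdrawal outcomes, pre-specify the post-vaping score as outcome and the same session's pre-vaping score as covariate. Split it into the person's mean and the deviation from it, so that between-person and within-person slopes are not mixed.
3. For these outcomes add schedule option and first or second session within visit, since a single session effect does not separate the two schedules.

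Cost: protocol and SAP wording, a few model terms, and a few minutes per session if the scales are not already in the opening slot. Sample size and visit schedule do not change.

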Utilizing a within-subjects, factorial design, 60 e-cig users (aged 21-25 years) will complete vaping sessions which will include a standardized, 5-minute, 10-puff vaping bout (30 seconds between each puff) followed by 30 minutes of ad libitum vaping. Prior to session one, participants will be asked to bring their own e-cig device and a full tank/pod to the first visit. In session one, participants will use their own e-cig and e-liquid. After visit 1, participants will take home a study e-cig device and 1 weighed pod pre-filled with study e-liquid (the participant was randomized to at the end of visit 1) to practice (20 puffs per day with the study device and until the participant feels comfortable) using the device before visit 2. Practice use with the study e-cig device and pre-filled pod will be verified based on data downloaded (via eScribe) from the device during visit 2. In the subsequent vape sessions, participants will use a study e-cig held at a constant wattage, and pre-filled with e-liquid of different nicotine form (free-base vs. nicotine salt), concentration (low-1% vs. high-5%), and flavoring (tobacco vs. menthol). There is no known commercial pair of nicotine liquids that differ only by nicotine form. For this study, we will prepare 8 e-liquids that differ by nicotine form, nicotine concentration, and flavor, simulating characteristics of popularly used nicotine liquids^{32,39}. E-liquids will be prepared from pure ($\geq 99\%$) S-(-)-nicotine; protonation and dilution of nicotine will be done using USP grade benzoic acid, and glycerol and propylene glycol, respectively. We will submit an Investigational Tobacco Product application to the U.S. FDA regarding the clinical use of the e-liquids. All sessions will be completed over nine visits for schedule Option A and 5 visits for schedule Option B. Study Schedule A consist of 9 separate visits and 9 separate vaping sessions. Study schedule B will consist of five separate visits (each visit will include up to 2 vaping sessions) each separated by a 3-hour washout period to allow nicotine levels to return to baseline. Each visit will be at least 48 hours apart. Participants will be required to report at least 12 hours abstinent from nicotine before each study visit. Participants will be told that their abstinence will be confirmed at the time of visit via blood plasma nicotine analysis. This is a partial bogus pipeline⁴⁰; 3mL venous blood sample will be collected for later analysis.; those with plasma nicotine levels $>3\text{ng/mL}$ at the time of their visit will be replaced post hoc with another participant. We conservatively estimate replacing 10% of participants. Measures of topography, nicotine uptake, abuse liability, subjective effects, and cardiovascular and pulmonary effects will be collected (see Table 1). Exposure to select toxicants, including nicotine and menthol in total particulate matter, and gas phase carbonyls and volatile organic compounds, will also be estimated post hoc using puff playback machine smoking.

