explain the study to the participant and answer any questions they may have. The participant will give an exhaled breath sample into the handheld CO monitor to determine if they are eligible to participate in the laboratory vaping session. If the participant's exhaled CO concentration ≤ 10 ppm, they are deemed eligible to participate further, and will be asked to read the informed consent form. Once all participant questions have been answered, the participant will be asked to sign their consent to participate in the study. Pregnancy exclusion will also be confirmed with a urine test. Participants will be asked to avoid eating (anything), drinking coffee, tea, sodas, juice, alcohol, and smoking (including any cigarette/nicotine replacements such as electronic cigarettes) at least 3 hours prior to their visit since that will affect the results of certain measures. Participants will not be allowed to eat or drink (other than water) during the vaping sessions, but will be provided a light snack prior to IV placement and the start of vaping sessions. Participants will be allowed to eat and drink during the 3-hour washout periods for Option B visits 2-5.

First, participants will complete background measures (Sociodemographic Measures, Tobacco Use History (including the Timeline Followback (TLFB) interview– week, month, lifetime and the Sensory E-Cigarette Expectancies Scale (SEES)⁴²), and the E-Cig Dependence (modified Cigarette Dependence Scale)⁴³. To measure nicotine uptake, a forearm venous catheter (placed by the research nurse) will be used to sample blood (~ 5 mL) as participants complete an initial 30-minute ad libitum vaping session using their own e-cig device and e-liquid. Blood will be collected at 4 time points (t=0, 5, 10, and 35 minutes) during each vaping session.

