All measures (see Table 1) are validated and have been used previously by our team. Sociodemographic measures and tobacco use history (including the Timeline Followback (TLFB) interview– week, month, lifetime and the Sensory E-Cigarette Expectancies Scale (SEES)⁴²) will be collected in addition to e-cig dependence using the modified Cigarette Dependence Scale⁴³. E-cig Abuse liability will be measured across several domains, including 1) E-cig puff topography to produce measures of puff count, puff duration, inter-puff-interval, puff flow rate, average puff volume, and total puff volume⁵⁰, 2) Subjective effects, including the Drug Effects/Liking Questionnaire and modified Cigarette Evaluation Questionnaire (mCEQ)^{51, 52}, 3) Behavioral economic demand using the E-Cigarette Purchase Task⁵³, and 4) E-cig craving/suppression of craving and withdrawal using the Tiffany-Drobes Questionnaire of Smoking Urges: Brief Form⁵⁴ and Minnesota Nicotine Withdrawal Scale⁵⁵. Nicotine uptake: a forearm venous catheter will be used to sample blood (~5 mL). Blood will be collected at 4 time points (t=0, 5, 10, 35 min) during each vaping session. E-liquid consumption: e-liquid containers for pods will be weighed (mg) before and after each vaping session. Toxicant exposure: to estimate toxicant exposure, the e-cig device, e-liquid, and participants' average puffing topography data for that e-liquid (across all participants) will be used to control a vaping machine. The e-cig aerosol produced will be collected on filters or in impingers for later analysis using high performance liquid chromatography, gas chromatography/mass spectrometry or similar methods of instrumental analysis. E-cig device characteristics, including device voltage, coil resistance, and pressure drop; and e-liquid characteristics including pH, nicotine concentration, and PG/VG ratio will be determined. Since participants will primarily use the study e-cig and e-liquid to determine exposures associated with the least and most intense puffing behaviors, topographies in the upper tertile will be averaged to produce a single topography, and likewise for the lowest tertile. Machine vaping will be conducted for each e-liquid type, using the associated human-derived puffing regimens, to estimate the range of tobacco toxicant exposure. Laboratory spirometry, airway inflammation, and airway reactivity⁴⁷⁻⁴⁹ will be measured. Laboratory spirometry will be conducted in a standing position and according to the recommendations of ATS Clinical Guidelines⁴⁷. Forced expiratory volume (FEV1), forced vital capacity (FVC), and FEV1/FVC. Airway inflammation will be assessed using exhaled nitric oxide via the NIOX VERO. The current literature shows immediate changes

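### Plasma nicotine is drawn four times per session, but the plan does not say which value is modelled, and its listed terms include no draw time, no session-within-participant effect and no t=0 value

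*Combined protocol and SAP*

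**What the plan says.** Section D.ii.2.a (Study Sessions) states: "Blood will be collected at 4 time points (t=0, 5, 10, and 35 minutes) during each vaping session". Section D.iii (Measures) repeats the schedule. Figure 1 in D.i puts the first draw in the start-of-session block, ahead of the puffing: "Surveys Respiratory Measures Cardiovascular Measures Blood Draw (0 min". Section D.ii describes the exposure as "a standardized, 5-minute, 10-puff vaping bout (30 seconds between each puff) followed by 30 minutes of ad libitum vaping". The 5-minute draw therefore follows a fixed puff count, and the 10- and 35-minute draws also reflect ad libitum use.

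Section E names the outcomes only by example: "various outcome measures (e.g., plasma nicotine, spirometry, flow-mediated dilation". It gives the terms as "Models will include relevant covariates (e.g., gender), a random effect for participant, main effects for nicotine form and concentration", together with "the interaction between nicotine form and concentration and nicotine form and flavor". Section E.ii adds "a fixed effect for session and a random effect for sequence will be included in all analyses". Section E.i says that carryover and period effects will be examined, without a method.

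The one stated use of a pre-exposure nicotine level is the abstinence check in D.ii. It is described per visit and leads to replacement of participants above 3 ng/mL. Under Option B, visits 2 to 5 each hold two vaping sessions separated by a 3-hour washout.

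**The concern.** Nicotine uptake is part of H1b and is to be tested at 0.01. A reader cannot tell whether the response is all four draws, one draw, a change from t=0, a peak or an area under the curve. These choices do not answer the same question, and they need different models.

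Two things are at stake. If the four draws are stacked, draws from one person in one session are correlated, and nothing in the list represents that. The fixed session term is a period effect shared by all participants, and the participant and sequence effects do not separate one session from another within a person. The t=0 draw, which the session's liquid cannot affect, would also be averaged into the liquid effect. If instead one value per session is used, the session's own t=0 value is collected but has no stated role. It matters most in Option B second sessions, where it may carry nicotine from the liquid vaped earlier that day.

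**Working it through.** **Inputs from the documents.** 60 completers (D.ii.1.a); eight study liquids, so eight study sessions; four draws per session; alpha 0.01; effect 0.5 SD of paired differences (E.i). The documents give no variances or correlations, so those below are assumptions shown over a range. Tests are taken as two-sided, since sidedness is not stated.

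**The plan's own figure.** E.i states 80% power for a main effect. A paired t-test with n = 60, d = 0.5 and alpha = 0.01 gives 88.2% (normal approximation: Φ(0.5√60 − 2.576) = 90.3%). By the t-test, 80% needs n = 51. The stated figure is not reproduced at 60, but this point does not rest on it. The 88.2% is the reference for the power comparison below.

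**Type I error if all four draws are stacked.** Let ρ be the share of within-participant per-draw variance that is common to a session. Let k be the variance of the four time means divided by that same per-draw variance. For the form contrast in a balanced 60 × 8 × 4 layout:

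true variance / assumed variance ≈ (1 + 3ρ) / (1 + k)

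type I error = 2 × [1 − Φ(2.576 / √ratio)]

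Example: for ρ = 0.5 and k = 0 the ratio is 2.5, 2.576/√2.5 = 1.629, and the error is 10.3%.

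| k | ρ = 0.2 | ρ = 0.5 | ρ = 0.8 |
|---|---|---|---|
| 0 (flat profile) | 4.2% | 10.3% | 16.2% |
| 1 | 0.4% | 2.1% | 4.8% |
| 2 | 0.04% | 0.5% | 1.6% |
| 4 | <0.01% | 0.03% | 0.2% |

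Simulation with 4,000 replicates per cell gave 4.4%, 12.5% and 17.3% in the k = 0 row, similar to or somewhat above the approximation. The two omissions pull in opposite directions. Leaving out session-within-participant makes the test liberal. Leaving out time inflates the residual and makes it conservative. They cancel when k = 3ρ.

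Adding a time term alone removes only the conservative part: simulated error is about 4.4%, 11–12% and 17–19% for ρ = 0.2, 0.5 and 0.8. With time and session both handled, or with one post-exposure mean or change from t=0 per session, simulated error was 0.8–1.3%.

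**Dilution.** If the liquid has no effect at t=0 and a common effect at the other three draws, the pooled contrast is 3/4 of the post-exposure effect. Simulation gave 0.302 against a true 0.40.

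**Power.** Let the post-exposure paired difference have mean 0.5 and SD 1, and let the t=0 difference have mean 0, SD s and correlation r with it. The pooled difference has mean 0.375 and SD √(0.5625 + 0.0625s² + 0.375rs). Power is for the paired t-test, n = 60, alpha 0.01:

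| s | r | pooled SD | d | power |
|---|---|---|---|---|
| 0.2 | 0 | 0.752 | 0.499 | 88% |
| 0.2 | 0.6 | 0.781 | 0.480 | 85% |
| 0.5 | 0 | 0.760 | 0.493 | 87% |
| 0.5 | 0.6 | 0.831 | 0.451 | 79% |
| 1 | 1 | 1.000 | 0.375 | 60% |

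The raw contrast always shrinks to 75%. The standardized effect, and so the power, falls much less unless t=0 varies about as much as the later draws and is strongly correlated with them.

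**The case against.** The strongest reply is that the plan never says four raw draws go into one model. Plasma nicotine appears in a list of examples, and the power statement in E.i, expressed in paired differences, fits one value per participant and condition. On that reading no time term and no session-within-participant effect is needed. This stands: the fault is an unspecified response, and the error rates above apply only if the draws are stacked.

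A reader might infer that the error rate for uptake is well above 0.01 as the plan is written. The documents do not support that. Plasma nicotine can be expected to rise while participants vape, a rise omitted from the model makes the test conservative, and no figure in the plan fixes the balance.

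A reader might also infer that power falls from 88% to 60%. That needs the SD to stay unchanged after pooling. Replacing participants above 3 ng/mL at the visit limits t=0 variation, at least in first sessions.

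Nor do the documents show that residual nicotine in general biases the liquid comparisons. Liquid order is randomized by Latin Square with a fixed session effect, so residual nicotine unrelated to the liquids is balanced in expectation. Adjustment for it is a matter of precision.

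Finally, the covariate list is open-ended and carryover is to be examined, so t=0 adjustment is unspecified rather than excluded. But an open list with only gender named does not commit the analysis to t=0, and the carryover check has no method. In Option B second sessions the residual can come from a study liquid used about three hours earlier, and a check described per visit does not clearly cover that t=0 value.

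**Conclusion.** The point holds as a gap in specification with a clear and nearly free improvement. It does not show that the uptake analysis is invalid.

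- **If the four draws are stacked with the listed terms:** the 1% level is not controlled. It runs from near 0% to about 17% over ρ from 0.2 to 0.8 and k from 0 to 4, all assumed values. The raw contrast falls to three quarters. Power is about 79% to 88% when t=0 differences have one-fifth to one-half of the post-exposure SD (correlation 0 to 0.6), and about 60% only in the extreme case of equal SD and perfect correlation.
- **If one value per session is used:** the test level is sound. What remains is lost precision, to the extent that t=0 predicts later values, and unadjusted residual nicotine from the earlier liquid in Option B second sessions. The documents do not allow either to be sized.

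On both readings, the choice among several plausible responses is left open until the data are in hand.

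**What to change.** State the plasma nicotine response in section E, in one of two ways.

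1. Model the 5-, 10- and 35-minute values with draw time, liquid factors by time, a session-within-participant random effect, and the session's own t=0 value as covariate, in addition to the terms already listed.
2. Analyse one pre-specified post-exposure summary per session with that session's t=0 value as covariate. Keep the 5-minute value, which follows the fixed 10-puff bout, separate from any value that includes ad libitum use, because a single area over 0–35 minutes would merge the two exposures.

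Under either option, state that the t=0 covariate is session-specific, so that each Option B second session uses its own pre-exposure draw. The cost is SAP wording and minor programming. All the values are already collected.
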